10.4 Appendix 4: Abbreviations

Abbreviation	Definition
ADHD	Attention-deficit hyperactivity disorder
AE	Adverse event
AESI	Adverse event of special interest
ALP	Alkaline phosphatase
ALT	Alanine aminotransferase
Anti-HCV	Hepatitis C antibodies
AST	Aspartate aminotransferase
AUC _{0-12h}	Area under the concentration-time curve from time 0 to 12 hours postdose
[REDACTED]	
[REDACTED]	
BMI	Body mass index
bpm	Beats per minute
BUN	Blood urea nitrogen
C _{max}	Maximum (peak) plasma concentration
CPK	Creatine phosphokinase
C-SSRS	Columbia-Suicide Severity Rating Scale
ECG	Electrocardiogram
eCRF	Electronic case report form
eICF	Electronic informed consent form
EoT	End-of-treatment
ET	Early termination
FDA	Food and Drug Administration
FOCBP	Females of childbearing potential
GCP	Good clinical practice
GGT	Gamma glutamyl transferase
HBsAg	Hepatitis B surface antigen
hCG	Human chorionic gonadotropin
HDL	High-density lipoprotein
HIV	Human immunodeficiency virus
IB	Investigator's Brochure
ICF	Informed consent form
ICH	International Council for Harmonisation
ICMJE	International Committee of Medical Journal Editors
ID	Identifier
IMP	Investigational medicinal product
IND	Investigational New Drug
IQ	Intelligence quotient
IR	Immediate-release
IRB	Institutional review board
IRE	Immediately reportable event
LDH	Lactic dehydrogenase
LDL	Low-density lipoprotein

Protocol 405-201-00037

Abbreviation	Definition
PD	Pharmacodynamic
PK	Pharmacokinetic
PQC	Product Quality Complaint
QTc	Corrected QT interval
QTcF	QT interval corrected for heart rate using Fridericia's formula
RBC	Red blood cell count
SAE	Serious adverse event
SR	Sustained-release
T4	Thyroxine
TDD	Total daily dose
TEAE	Treatment-emergent adverse event
t_{max}	Time to maximum concentration
TSH	Thyroid-stimulating hormone
ULN	Upper limit of normal
VAS	Visual analogue scale
WBC	White blood cell count
XR	Extended-release

Protocol 405-201-00037

10.5 Appendix 5: Criteria for Identifying Laboratory Values of Potential Clinical Relevance

Laboratory Tests	Criteria (Normal Ranges) for Subjects 9 - 12 Years Old ^{a,b}
Chemistry	
AST	$\geq 2 \times \text{ULN}$
ALT	$\geq 2 \times \text{ULN}$
ALP	$\geq 2 \times \text{ULN}$
BUN	$\geq 24 \text{ mg/dL} (\leq 4 \text{ mg/dL} \text{ or } \geq 24 \text{ mg/dL})$
Creatinine	$\geq 0.7 \text{ mg/dL} (\leq 0.2 \text{ mg/dL} \text{ or } \geq 0.7 \text{ mg/dL})$
Uric acid	$\geq 6.7 \text{ mg/dL} (\leq 1.6 \text{ mg/dL} \text{ or } \geq 6.7 \text{ mg/dL})$
Bilirubin (total)	$\geq 1.6 \text{ mg/dL} (\leq 0.2 \text{ mg/dL} \text{ or } \geq 1.6 \text{ mg/dL})$
CPK	$\geq 2 \times \text{ULN}$
Prolactin	$\geq 21.00 \text{ ng/dL} (\leq 2.63 \text{ ng/dL} \text{ or } \geq 21.00 \text{ ng/dL})$
Hematology	
Hematocrit	$\leq 33\% (\leq 33\% \text{ or } \geq 44\%)$
Hemoglobin	$\leq 11.2 \text{ g/dL} (\leq 11.2 \text{ g/dL} \text{ or } \geq 15.5 \text{ g/dL})$
White blood count	$\leq 4.35 \times 10^3/\mu\text{L} (\leq 4.35 \times 10^3/\mu\text{L} \text{ or } \geq 13.65 \times 10^3/\mu\text{L})$
Eosinophils	$\geq 4.8\%$
Neutrophils	$\leq 40.5\% (\leq 40.5\% \text{ or } \geq 75.0\%)$
Absolute neutrophil count	$\leq 1.00 \times 10^3/\mu\text{L} \text{ or } \geq 9.00 \times 10^3/\mu\text{L}$
Platelet count	$\leq 130 \times 10^3/\mu\text{L} (\leq 130 \times 10^3/\mu\text{L} \text{ or } \geq 570 \times 10^3/\mu\text{L})$
Urinalysis	
Protein	Change from baseline
Glucose	Presence
Additional Criteria	
Chloride	$\leq 94 \text{ mEq/L} \text{ or } \geq 112 \text{ mEq/L}$
Potassium	$\leq 3.3 \text{ mEq/L} \text{ or } \geq 5.2 \text{ mEq/L}$
Sodium	$\leq 132 \text{ mEq/L} \text{ or } \geq 148 \text{ mEq/L}$
Calcium	$\leq 8.3 \text{ mg/dL} \text{ or } \geq 10.9 \text{ mg/dL}$
Glucose	
Fasting	$\geq 100 \text{ mg/dL} (\leq 70 \text{ mg/dL} \text{ or } \geq 100 \text{ mg/dL})$
Nonfasting	$\geq 139 \text{ mg/dL} (\leq 59 \text{ mg/dL} \text{ or } \geq 139 \text{ mg/dL})$
Total cholesterol, fasting	$\geq 217 \text{ mg/dL} (\leq 97 \text{ mg/dL} \text{ or } \geq 217 \text{ mg/dL})$
LDL cholesterol, fasting	$\geq 130 \text{ mg/dL}$
HDL cholesterol, fasting	$\leq 34 \text{ mg/dL} (\leq 34 \text{ mg/dL} \text{ or } \geq 75 \text{ mg/dL})$
Triglycerides, fasting	$\geq 131 \text{ mg/dL} (\leq 30 \text{ mg/dL} \text{ or } \geq 131 \text{ mg/dL})$

^aThe recommended criteria represented in this table are intended to identify on-treatment outside of normal values that could potentially be clinically relevant. Variations based on local laboratory ranges may need to be considered.

^bInformation adapted from: 1. Soghier L, Pham K, Rooney S. Reference Range Values for Pediatric Care. The American Academy of Pediatrics. 2014; 2. Hughes HK, Kahl LK. The Johns Hopkins Hospital: The Harriet Lane Handbook. 21st edition. 2015; 3. Covance central laboratory reference ranges, 2019.

Protocol 405-201-00037

10.6 Appendix 6: Criteria for Identifying Vital Signs of Potential Clinical Relevance

Variable	Criterion Value ^a	Change Relative to Baseline ^a
Heart rate at rest ^b	< 60 bpm or > 110 bpm	Increase or decrease of ≥ 15 bpm
Systolic blood pressure ^c		
School-age (6 to 9 years old)	< 85 mmHg or > 115 mmHg	Increase or decrease of ≥ 20 mmHg
Preadolescent (10 to 12 years old)	< 90 mmHg or > 120 mmHg	Increase or decrease of ≥ 15 mmHg
Diastolic blood pressure ^c		
School-age (6 to 9 years old)	< 50 mmHg or > 80 mmHg	Increase or decrease of ≥ 15 mmHg
Preadolescent (10 to 12 years old)	< 60 mmHg or > 80 mmHg	Increase or decrease of ≥ 15 mmHg
Orthostatic hypotension	≥ 30 mmHg decrease in systolic blood pressure and/or a decrease of ≥ 20 mmHg in diastolic blood pressure after at least 3 minutes of standing compared to the previous supine blood pressure	Not applicable (baseline status not considered)
Orthostatic tachycardia	≥ 25 bpm increase in heart rate from supine to standing	Not applicable (baseline status not considered)
Weight	Not applicable	Increase or decrease of $\geq 25\%$

bpm = beats per minute.

^aThe criterion value and change relative to baseline represented in this table are intended to identify on-treatment values outside of normal changes and that could potentially be clinically relevant. In order to be identified as potentially clinically relevant, the on-treatment value must meet the “Criterion Value” and also represent a change from the subject’s baseline value of at least the magnitude shown in the “Change Relative to Baseline” column. When evaluating these values, the emotional state of the subject must be taken into consideration (eg, crying, screaming) and documented as applicable.

^bInformation adapted from: Hughes HK, Kahl LK. The Johns Hopkins Hospital: The Harriet Lane Handbook. 21st edition. 2015.

^cInformation adapted from: Flynn JT, Kaelber DC, Baker-Smith CM, et al. Clinical Practice Guideline for Screening and Management of High Blood Pressure in Children and Adolescents: American Academy of Pediatrics Subcommittee on Screening and Management of High Blood Pressure in Children. Pediatrics. 2017;140(3):1-72.

Protocol 405-201-00037

10.7 Appendix 7: Criteria for Identifying ECG Measurements of Potential Clinical Relevance¹³

Variable	Criterion Value ^a	Change Relative to Baseline ^a
Rhythm		
Sinus tachycardia ^b	≥ 110 bpm	increase of ≥ 15 bpm
Sinus bradycardia ^c	≤ 60 bpm	decrease of ≥ 15 bpm
Supraventricular premature beat	all	not present → present
Ventricular premature beat	all	not present → present
Supraventricular tachycardia	all	not present → present
Ventricular tachycardia	all	not present → present
Atrial fibrillation	all	not present → present
Atrial flutter	all	not present → present
Conduction		
1 atrioventricular block	PR ≥ 200 msec	increase of ≥ 50 msec
2 atrioventricular block	all	not present → present
3 atrioventricular block	all	not present → present
Left bundle-branch block	all	not present → present
Right bundle-branch block	all	not present → present
Pre-excitation syndrome	all	not present → present
Other intraventricular conduction block ^d	QRS ≥ 120 msec	increase of ≥ 20 msec
Infarction		
Acute or subacute	all	not present → present
Old	all	not present → present
		≥ 12 weeks post trial entry
ST/T Morphological		
Myocardial ischemia	all	not present → present
Symmetrical T-wave inversion	all	not present → present
Increase in QTc		
< 12 years old	QTcF ≥ 450 msec	increase of 60 msec
≥ 12 years old	QTcF ≥ 460 msec	from baseline

QTc = corrected QT interval.

^aThe criterion value and change relative to baseline represented in this table are intended to identify on-treatment values outside of normal changes and that could potentially be clinically relevant. In order to be identified as potentially clinically relevant, the on-treatment value must meet the “Criterion Value” and also represent a change from the subject’s baseline value of at least the magnitude shown in the “Change Relative to Baseline” column. When evaluating these values, the emotional state of the subject must be taken into consideration (eg, crying, screaming) and documented as applicable.

^bNo current diagnosis of supraventricular tachycardia, ventricular tachycardia, atrial fibrillation, atrial flutter, or other rhythm abnormality.

^cNo current diagnosis of atrial fibrillation, atrial flutter, or other rhythm abnormality.

^dNo current diagnosis of left bundle branch or right bundle branch block.

Protocol 405-201-00037

10.8 Appendix 8: Protocol Amendments

The investigator will not make any changes to this protocol without the sponsor's prior written consent and subsequent approval/favorable opinion by the IRB. Any permanent change to the protocol, whether an overall change or a change for specific trial site(s), must be handled as a protocol amendment. Any amendment will be written by the sponsor. Each amendment will be submitted to the IRB, as required by local regulations. Except for "administrative" or "nonsubstantial" amendments, investigators will wait for IRB approval/favorable opinion of the amended protocol before implementing the change(s). Administrative amendments are defined as having no effect on the safety of subjects, conduct or management of the trial, trial design, or the quality or safety of IMP(s) used in the trial. A protocol change intended to eliminate an apparent immediate hazard to subjects should be implemented immediately after agreement by the sponsor and investigator, followed by IRB notification within local applicable timelines. The sponsor will submit protocol amendments to the applicable regulatory agencies within local applicable timelines.

When the IRB, investigators, and/or the sponsor conclude that the protocol amendment substantially alters the trial design and/or increases the potential risk to the subject, the currently approved written ICF and assent form will require similar modification. In such cases, after approval/favorable opinion of the new ICF and assent form by the IRB, repeat written informed consent/assent will be obtained from subjects enrolled in the trial and their guardian or legally acceptable representative before expecting continued participation and before the amendment-specified changes in the trial are implemented.

Protocol 405-201-00037

Protocol 405-201-00037

- [REDACTED]

Protocol 405-201-00037

11 References

- ¹ Sayal K, Prasad V, Daley D, Ford T, Coghill D. ADHD in children and young people: prevalence, care pathways, and service provision. *Lancet Psychiatry*. 2018;5: 175-186.
- ² Connor DF. Preschool attention deficit hyperactivity disorder: a review of prevalence, diagnosis, neurobiology, and stimulant treatment. *J Dev Behav Pediatr*. 2002;23:S1-S9.
- ³ Egger HL, Angold A. Common emotional and behavioral disorders in preschool children: presentation, nosology, and epidemiology. *J Child Psychol Psychiatry*. 2006;47:313-337.

This statistical analysis plan (SAP) documents the statistical methodology and data analysis algorithms and conventions to be applied for the analysis of clinical trial data of trial 405-201-00037 for centanafadine. The current version of SAP is based on protocol version 3.0 dated on 23 Jul 2019 and final SAP will be consistent with the final version of the protocol.

2 Trial Objectives

Primary Objectives:

To characterize the single-dose concentration-time profile from 0 to 12 hours of centanafadine in pediatric subjects (9 to 12 years, inclusive) with attention-deficit hyperactivity disorder (ADHD).

Other Objectives:

- To assess the safety and tolerability of centanafadine XR in pediatric subjects.
- To assess the ability of pediatric subjects to swallow the centanafadine XR capsule.
- [REDACTED]
- [REDACTED]
- To assess centanafadine concentrations 24 hours postdose for evaluation of the potential for accumulation following multiple doses.
- To compare the PK of centanafadine after administration of the intact capsules or the capsule contents sprinkled on to applesauce.

3 Trial Design

3.1 Type/Design of Trial

This is a pilot phase 2a, multicenter, open-label, single-dose trial in pediatric subjects (9 to 12 years, inclusive) with a documented history of ADHD and confirmation of an ADHD prescription medication. This trial consists of a screening period (Day -21 to Day -2), check-in (Day -1 or Day 1), 2-day treatment period (Day 1: dosing, Day 2: end of-treatment [EoT]), and a safety follow-up telephone call 7 (+ 2) days after dosing (Day 8). The screening period may be extended if additional time is needed to complete screening procedures, upon discussion with and approval by the medical monitor.

Written informed consent will be freely obtained from all subjects' guardian(s) or legally acceptable representative(s), as applicable for local laws. Written informed assent will be freely obtained from all subjects.

Protocol 405-201-00037

Eligible subjects will check-in either on Day -1 or Day 1, based on the investigator's decision. A single dose of centanafadine will be administered either as intact capsules or the capsule contents sprinkled on a tablespoon of applesauce on Day 1 in the morning.

[figure not shown]
[REDACTED] Pharmacokinetic

and safety assessments will be performed for approximately 24 hours postdose. Subjects may be released from the clinic after PK sample collection at 12 hours postdose to return the following morning or may remain in the clinic until 24 hours postdose, based on the investigator's decision. Subjects released on Day 1 will return to the clinic on Day 2 between 22 to 26 hours postdose for an outpatient visit, which will include EoT assessments and one PK sample. In-clinic subjects may leave the clinic on Day 2 after EoT assessments and PK sampling are complete.

Subjects and/or their caregivers will be contacted by telephone 7 days after dosing to assess any new or ongoing AEs and to record concomitant medications.

The trial design schematic is displayed in [Figure 3.1-1](#).

Figure 3.1-1 Trial Design Schematic

ET = early termination; EoT = end of treatment.

^a The screening period may be extended if additional time is needed to complete screening procedures, upon discussion with and approval by the medical monitor.

3.2 Trial Treatments

The ability of a subject to swallow the intact capsules will be assessed during the screening period with empty capsules. Based on this assessment, subjects will either be instructed to take the centanafadine capsules intact or the capsule contents sprinkled on a tablespoon of applesauce. An attempt will be made to administer the intact capsules to approximately half of the subjects and approximately half of the subjects will be administered the capsule contents sprinkled on a tablespoon of applesauce.

Centanafadine will be supplied as 1 capsule containing a 50-mg dose as [REDACTED] beads and 1 capsule containing a 5-mg dose as IR beads for a total centanafadine dose of 55 mg. Both of the intact capsules or the capsule contents sprinkled on a tablespoon of applesauce will be taken orally in the morning [REDACTED]
[REDACTED] following a minimum 8-hour fast. [REDACTED]
[REDACTED]
[REDACTED]
[REDACTED]
[REDACTED]
[REDACTED]

3.3 Trial Population

The trial population will consist of males and females, aged 9 to 12 years (inclusive), who have a documented history of ADHD and confirmation of an ADHD prescription medication.

Up to 12 subjects may be treated in the trial. Subjects who discontinue for a reason other than a safety-related event may be replaced at the discretion of the sponsor.

4 Sample Size

Since this is an exploratory trial, no formal sample size calculations will be performed. Up to 12 subjects may be treated depending on the concentration data and the number of subjects completing through 24 hours.

5 Statistical Analysis Sample

5.1 Enrolled Analysis Set

The enrolled analysis set includes all subjects who have eligibility to enroll in the trial based on screening process.

Protocol 405-201-00037

5.2 Safety Analysis Set

The safety analysis set includes all subjects who receive the single dose of centanafadine.

5.3 Pharmacokinetic (PK) Analysis Set

The PK analysis set includes all subjects who receive the single dose of centanafadine and have at least 1 postdose evaluable plasma concentration.

5.4 Handling of Missing Data

No data imputation will be performed for missing PK data in this trial. The handling of concentrations below the lower limit of quantitation will be according to the sponsor's data handling processes.

6 Primary and Secondary Outcome Variables

6.1 Primary Endpoints

The following primary endpoints will be evaluated:

- C_{\max} of centanafadine
- t_{\max} of centanafadine
- AUC_{0-12h} of centanafadine

6.2 Other Outcome Endpoints

The following other endpoints will be evaluated:

- Reported AEs, vital signs, body weight, ECGs, clinical laboratory tests, physical examinations, and the C-SSRS.
- Ability to swallow the centanafadine XR capsule.

6.3 Other PK Endpoints

The following PK endpoints will be evaluated:

- Centanafadine concentrations at 24 hours postdose

Protocol 405-201-00037

- PK parameters will be estimated (tmax, Cmax, and [REDACTED]) for EB 10601 (metabolite of centanafadine) [REDACTED].

- [REDACTED]
[REDACTED]

7 Disposition and Demographic Analysis

7.1 Subject Disposition

The number of subjects who have been screened, the number of subjects who are treated, the number of subjects who discontinue from the trial, and the subjects who complete the trial will be tabulated for total subjects. In addition, the assignment based on capsule swallow test during screening period will also be presented by intact capsule and capsule contents sprinkled on applesauce.

The number and percentage of subjects who discontinue are to be summarized by reason for discontinuation and mode of administration (intact capsules or capsule contents sprinkled on a tablespoon of applesauce) for the enrolled sample.

7.2 Demographic and Baseline Disease Characteristics

Baseline demographic characteristics include age, race, ethnicity, sex, weight, height, and BMI. Baseline disease characteristics include history of ADHD, history of allergy. Summary statistics will consist of mean, median, minimum, maximum, and standard deviation (SD) for continuous variables and tabulations of frequency distributions for categorical variables. The summary will be based on the enrolled sample and by mode of administration (intact capsules or capsule contents sprinkled on a tablespoon of applesauce).

7.3 Medical History

Listings for general medical history, surgical history, ADHD history, and psychiatric history will be provided. The listings will be based on the safety sample and by mode of administration (intact capsules or capsule contents sprinkled on a tablespoon of applesauce).

7.4 Treatment Compliance

The time and dose of each investigation medical product (IMP) administration will be recorded on the source documents and on the eCRF. Treatment compliance will be presented by mode of administration in a listing.

Protocol 405-201-00037

7.5 Concomitant Medication

The proportion of subjects taking concomitant medications will be tabulated by drug classification using WHODrug B3G (March 2019) for all enrolled subjects. Concomitant medications taken prior to dosing, taken on Day 1 dosing, taken after Day 1 dosing will be presented by mode of administration. In addition, listings of concomitant medications will also be provided.

7.6 Protocol Deviations

Any major protocol deviation will be recorded in the eCRF along with the start date and details of the deviation. A subject listing will be provided describing the deviation date and reason for each subject.

8 Pharmacokinetic Analysis

A noncompartmental analysis will be performed. Plasma concentrations of centanafadine and metabolite(s) will be summarized by time point and mode of administration (intact capsules or capsule contents sprinkled on a tablespoon of applesauce). The PK parameters will be summarized by analyte and mode of administration using descriptive statistics.

No inferential statistical analysis will be conducted.

The following PK parameters will be summarized:

- Maximum (peak) plasma concentration (C_{max}) of centanafadine
- Time to maximum concentration (t_{max}) of centanafadine
- Area under the concentration-time curve from time 0 to 12 hours postdose (AUC_{0-12h}) of centanafadine
- Centanafadine concentration at 24 hours postdose

A large rectangular area of the page is completely blacked out, indicating redacted content. It spans from approximately [171, 670] to [870, 890].

Protocol 405-201-00037

10 Safety Analyses

All the following safety analyses will be performed for the safety sample.

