2.1 Trial Rationale

Currently, the PK of centanafadine administered as IR/XR capsules is being evaluated in adults. It is possible that the PK (particularly absorption) of centanafadine following administration of the XR formulation may be different in children as compared to adults due to physiological differences in the gastrointestinal tract. Therefore, the primary purpose of this trial is to evaluate the PK of centanafadine [REDACTED] following administration of centanafadine capsules in pediatric subjects (9 to 12 years, inclusive) with ADHD and determine if the XR formulation is appropriate for further evaluation.

[figure not shown]
[figure not shown]

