4.3 Dosing Rationale

In adults, dosing is started at a 200 mg TDD administered in divided doses, 5 hours apart, using SR tablets; this regimen has been well tolerated. The 200 mg dose of [REDACTED] produced centanafadine concentrations approximately 75% of the 200 mg TDD of SR. In this trial, a dose of 5 mg of IR beads and 50 mg of [REDACTED] beads will be administered, as the approximate median weight of 10- and 11-year-old pediatric subjects is 35 kg, based on the Centers for Disease Control and Prevention (CDC) growth charts.¹⁰ As 75 kg is the approximate weight of adults from phase 1 and phase 2 trials, the expected centanafadine concentrations will be half of those observed in the PK Trial 405-201-00007. The same amount of dose will be administered to all subjects.

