8.7.2 Physical Examination

A complete physical examination will be performed at the time points described in the schedule of assessments ([Table 1.3-1](#)). The complete physical examination will include height (screening only), weight, and calculation of body mass index (BMI) as well as assessment of the head, eyes, ears, nose, and throat; thorax; abdomen; skin and mucosae; neurological; and extremities. Directed physical examinations in response to reported AEs will be conducted as necessary.

Protocol 405-201-00037

Whenever possible, the same individual should perform all physical examinations for any individual subject throughout the course of the trial. Individuals performing the physical examination must be permitted to do so by local regulations, must be listed on the Food and Drug Administration (FDA) Form 1572 as principal investigator or subinvestigator, and must be listed on the trial site delegation of authority form as performing this function.

Any post-screening abnormalities considered by the investigator to be clinically significant are to be recorded as AEs on the AE eCRF.

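### Does summarising PK only by mode of administration, with no named all-subjects summary, leave the primary objective unanswered?

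*SAP*

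**What the plan says.** The primary objective in SAP 2 reads "To characterize the single-dose concentration-time profile from 0 to 12 hours of centanafadine in pediatric subjects (9 to 12 years, inclusive"), with ADHD. It makes no reference to how the capsules are taken. Protocol 2.1 gives the wider purpose, which includes to "determine if the XR formulation is appropriate for further evaluation".

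The comparison of the two modes is a separate item under the other objectives in SAP 2: "To compare the PK of centanafadine after administration of the intact capsules or the capsule contents sprinkled on to applesauce".

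Mode is not randomised. SAP 3.2 assigns it from a capsule swallow test at screening and adds: "An attempt will be made to administer the intact capsules to approximately half of the subjects". The sprinkled contents go to the other half. The number treated is capped at 12 (SAP 4, Protocol 9.1), with no formal sample size calculation.

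For the analysis, SAP 8 groups concentrations by sampling time and mode, and for the parameters says: "The PK parameters will be summarized by analyte and mode of administration using descriptive statistics". It rules out inferential analysis and then lists Cmax, tmax and AUC0-12h without repeating any grouping. Protocol 9.4.3.2 and the synopsis match this. Redacted text follows the list in all three places, and the visible SAP goes from section 8 straight to section 10.

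**The concern.** The grouping named in SAP 8 fits the secondary question (intact against sprinkled) better than the primary one (the profile in 9 to 12 year-olds). Elsewhere the SAP does ask for totals: SAP 7.1 tabulates disposition over all subjects, and SAP 7.5 tabulates concomitant medication over all enrolled subjects before turning to mode. SAP 8 has no such words. A programmer working literally would therefore produce two PK columns and no third.

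If so, the report would carry two small-group descriptions of each primary endpoint and no overall figure. An even split is only attempted, so one column could hold fewer than 6 children. Some overall statistics could be rebuilt from the published columns, but a median could not, and the median is a natural summary for tmax, a primary endpoint.

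A side worry is that the columns may not be alike. Mode follows swallowing ability, and Protocol 4.3 says "The same amount of dose will be administered to all subjects", so a difference in body weight between modes would carry into exposure.

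**Working it through.** **Is there a figure to reproduce?** No. The documents give no precision target, CV or power calculation. The only count is the split: 12 × 0.5 = 6 per mode, if the ceiling of 12 is reached and the attempted split succeeds.

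**What is lost without a total column?** The two columns partition the PK analysis set, so no child's data drop out. With by-mode sizes n1, n2 and means m1, m2, the overall mean is (n1·m1 + n2·m2)/(n1 + n2). The same weighting on the log scale gives an overall geometric mean if by-mode geometric means are shown. The overall minimum and maximum are the more extreme of the two column values. Only order statistics such as the median need the individual data, which the sponsor holds.

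**How much precision would pooling show?** This is illustrative. The CVs are assumed because the documents give none, and the visible plan calculates no intervals. On the log scale the SD is s = √ln(1 + CV²), the half-width is h = t(0.975, n−1)·s/√n, and the interval is the geometric mean ×/÷ exp(h).

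For CV 40%, s = √ln(1.16) = 0.3853:

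| n | h | factor |
|---|---|---|
| 4 | 0.6130 | 1.85 |
| 6 | 0.4043 | 1.50 |
| 8 | 0.3221 | 1.38 |
| 12 | 0.2448 | 1.28 |

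The ratio of half-widths at 6 and 12 is 0.4043/0.2448 = 1.65. It is the same at every CV, because s cancels. For n = 6 against n = 12, the factors are 1.36 against 1.21 at CV 30%, and 1.64 against 1.35 at CV 50%.

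**What would the pooled figure mean?** It mixes two modes in whatever proportion the swallow test produces. If the true ratio between modes is R, moving from a 6:6 to an 8:4 split multiplies the overall geometric mean by R^(8/12 − 6/12) = R^(1/6) when the mode with higher exposure gains children:

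- R = 1.25: 1.25^(1/6) = 1.038, a shift of 3.8%.
- R = 1.5: 1.5^(1/6) = 1.070, a shift of 7.0%.

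The pooled spread also absorbs the difference between modes. At 6:6 the overall SD is √(s² + [36/(12·11)]·(ln R)²). At CV 40% this is 0.4025 for R = 1.25 (factor 1.29) and 0.4396 for R = 1.5 (factor 1.32). Pooling is still tighter than 6 alone, but its centre depends on the split. The by-mode columns are what tell a reader whether pooling is sensible.

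**Would a weight imbalance be hidden?** No. Weight is among the baseline characteristics in SAP 7.2, which says "The summary will be based on the enrolled sample and by mode of administration".

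**The case for a change.** The strongest case for a change is that the primary objective should have its own prespecified summary. The grouping sentence is complete and identical in three places, the SAP names totals when it wants them, and an overall median tmax cannot be recovered from two columns. Adding a total costs one sentence and one column, and naming it before the data are seen avoids a later choice.

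Most of the factual part stands: the visible text names no total, and the contrast with SAP 7.1 and 7.5 is real. The inference to a defect does not. Grouping by mode does not mean only by mode, and the parameter list that follows carries no grouping. The redacted text after the lists, and the unseen SAP section 9, may hold a total; text lost to redaction cannot be counted against the plan. The primary objective asks for a profile to be characterised and does not ask for one pooled estimate. Two profiles covering every child can do that. They may do it better, since Protocol 2.1 is concerned with absorption, which opening the capsules might affect. With no test, threshold or decision rule attached to a pooled value, a later total column gives little room for selective choice: it is the same endpoints over the whole PK analysis set.

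**Conclusion.** No change to the plan is needed. At most, SAP 8 leaves a table column unnamed, and an analyst can add an all-subjects column beside the by-mode columns from data already in hand. Followed as written, the plan gives valid descriptive summaries for every child in the PK analysis set, and no result or conclusion would be wrong.

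The largest effect is one of presentation. With 12 children split evenly, each column's log half-width would be 1.65 times that of the whole group, if intervals were calculated at all. That rests on log-normal exposure and equal spread in the two modes. The factors of 1.28 and 1.50 rest further on an assumed CV of 40%. They describe intervals the visible plan does not produce, in a trial with no precision target to miss. A pooled value would also have its own weakness, moving by 3.8% to 7.0% with the achieved split if the modes differ by a ratio of 1.25 to 1.5. The documents show no weight imbalance between modes, and the planned baseline table would reveal one.
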